8.3 Exploratory Endpoints

CD8 tumor infiltrating lymphocytes (TILs) will be assessed by % of tumor showing infiltration and calculation of CD8 TIL density in the pre- and post-treatment biopsy specimens. An increase in the TIL density will be termed a TIL-response and correlated with TCIP response using Pearson or Spearman rank correlation coefficients.

Presence of additional pathologic markers, including CD3, CD4, CD68, and CD20 will be assessed in pre- and post-treatment tissue samples. Results will be descriptive and presented in tabular form. Changes in PD-L1 expression compared between the pre- and post-treatment tissue samples will be determined using IHC and mass spectrometry. Ordinal IHC data will be assessed using the

Wilcoxon signed-rank test. Changes in other continuous immune response and biomarker values will be analyzed using paired t-tests.

Analysis of variance for repeated measures will be performed to evaluate changes in serum mesothelin and osteopontin levels over time.

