5.4 Adjuvant Nivolumab and Ipilimumab

Following surgery, patients will have 6-8 weeks of recovery prior to the initiation of adjuvant immunotherapy. Cross-sectional imaging will be obtained prior to starting adjuvant therapy and will be repeated every 6 weeks while on therapy. Adjuvant immunotherapy with nivolumab and ipilimumab will be administered according to the same dosing and schedule as it was given in the neoadjuvant phase, but with the first cycle to include nivolumab alone.

The first 2 cycles in the adjuvant phase will include nivolumab delivered at a dose of 3 mg/kg over 30 minutes every 21 days via IV infusion on day 1 and day 22 of each 42-day cycle for 4 doses (2 cycles) and ipilimumab delivered at a dose of 1 mg/kg over 30 minutes every 42 days via IV infusion on day 22 of each 42-day cycle for 2 doses (2 cycles). When given on the same day as nivolumab, ipilimumab is to be given following nivolumab infusion. Following these first 2 adjuvant cycles, nivolumab will be delivered alone at the same dose, route, and rate every 21 days on days 1 and 22 of each 42-day cycle, continuing until 1 year post-operatively.

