7.1.2 Flow Chart for Adjuvant and Post-Treatment Phases

Table 3. Trial Flow Chart of Adjuvant and Post-Treatment Phases

Trial Period:	Adjuvant Therapy Phase								End of Treatment	Post-Treatment Phase			
	Treatment Week/Title:		C1 D1	C1 D22	C2 D1	C2 D22	C1 D1	C1 D22	C2 D1	C2 D22	Safety Follow-up	Follow Up Visits	Survival Follow-Up
Scheduling Window (Days) ^c :		± 3	± 3	± 3	± 3	± 3	± 3	± 3	± 3	At time of Discon	30 days post discon	Every 12 wks post discon	Every 12 weeks
Nivolumab Administration	X	X	X	X	X	X	X	X	X				
Ipilimumab Administration		X		X									
Prior and Concomitant Medication Review	X	X	X	X	X	X	X	X	X	X			
Post-study anticancer therapy status									X				
Survival Status									X	X	X	X	
Review Adverse Events	X	X	X	X	X	X	X	X	X	X	X	X	X
Full Physical Examination	X	X	X	X	X	X	X	X	X				
Vital Signs and Weight	X	X	X	X	X	X	X	X	X				
ECOG Performance Status	X	X	X	X	X	X	X	X	X				
EORTC QOL C30	X		X		X		X		X	X			
Laboratory Parameters													
CBC with Differential	X	X	X	X	X	X	X	X					
Comprehensive Serum Chemistry Panel	X	X	X	X	X	X	X	X					
TSH (reflex T3, T4 if abnormal)	X		X		X		X						
Efficacy Measurement													
Tumor Imaging with CT scan every 12 weeks ^c	X		X		X		X						
CA-125	X		X		X		X						
Circulating tumor cells	X		X		X		X						
Correlative Lab													
Correlative Studies Blood Collection ^{a,b}	X				X				X				
a. Both tumor imaging and correlative studies to be repeated after every 6 weeks. b. Serum mesothelin and osteopontin will be obtained at the times of tumor imaging and upon tumor progression. c. For CT scans, the scheduling window is +/- 7 days													

The Trial Flow Chart summarizes the trial procedures to be performed at each visit. Individual trial procedures are described in detail below. It may be necessary to perform these procedures at unscheduled time points if deemed clinically necessary by the investigator.

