7.11 Tumor Imaging and Assessment of Disease

CT or MRI scans will be obtained at baseline. After completion of neoadjuvant nivolumab + ipilimumab treatment a CT or MRI imaging will again be repeated after completion of surgery (prior to starting adjuvant immunotherapy), and repeated every 6 weeks while on adjuvant therapy and every 3 months for 1 year after completing treatment.

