7.16 Survival Follow-up

Once a subject experiences confirmed disease progression or starts a new anti-cancer therapy, the subject moves into the survival follow-up phase and should be contacted by telephone every 12 weeks to assess for survival status until death, withdrawal of consent, or the end of the study, whichever occurs first.

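### Repeated-measures ANOVA for serum mesothelin and osteopontin is named without visits, model form or missing-data rule; run classically over all visits, it would be a complete-case analysis selected on outcome

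*Combined protocol and SAP*

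**What the plan says.** The analysis of these two markers is one sentence in Section 8.3: "Analysis of variance for repeated measures will be performed to evaluate changes in serum mesothelin and osteopontin levels over time". It does not say which visits enter, whether the model is classical or mixed, what covariance is assumed, or what happens to a patient with a gap.

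The sampling rule is in Table 3, footnote b (Section 7.1.2), and is repeated under Table 2: "Serum mesothelin and osteopontin will be obtained at the times of tumor imaging and upon tumor progression". The number of repeated measures therefore follows the scans. Sections 1.1, 5.3 and 5.4 and Table 2 place scans at screening, after neoadjuvant treatment and before adjuvant treatment. Section 7.11 then has them "repeated every 6 weeks while on adjuvant therapy and every 3 months for 1 year after completing treatment". Section 5.4 has nivolumab "continuing until 1 year post-operatively".

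Table 3 is not consistent on the interval. Its row label reads "Tumor Imaging with CT scan every 12 weeks", while its footnote a reads "Both tumor imaging and correlative studies to be repeated after every 6 weeks".

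Two follow-up rules decide who still has samples. Under Section 7.15, a patient who stops treatment without progression is imaged every 3 months. Under Section 7.16, the rule for patients who progress or begin other cancer treatment is that "the subject moves into the survival follow-up phase and should be contacted by telephone every 12 weeks to assess for survival status".

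Section 4.7 refers missing data to prespecified handling guidelines. Section 8 contains none.

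**The concern.** In its classical form, repeated-measures ANOVA needs a value for every patient at every time point in the model. A patient with one gap is removed along with all of that patient's other samples. Here gaps arise by design as well as by chance. Patients who progress move to telephone contact, patients whose progression precludes surgery (foreseen in Section 2.2, objective 2) lack the later visits, and patients who stop treatment early are sampled on different weeks from those still on it.

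Patients who progress would therefore be the ones most reliably excluded. If either marker behaves differently in them, the estimated time course would describe those who stayed progression-free through the last visit in the model, not the treated group. The sample at progression falls on no scheduled visit, so a balanced layout has no cell for it, although the protocol goes to the trouble of collecting it.

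**Working it through.** The documents give no figure for this analysis, so there is nothing of the plan's own to reproduce. The check asks how much a complete-case analysis would lose.

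**Inputs from the documents.** n = 37 (Section 8.1). Sampling times follow the scans. The second neoadjuvant nivolumab dose is on day 22, about week 3, and surgery is 2–6 weeks later, so about week 7. Adjuvant treatment starts 6–8 weeks after surgery, so about week 14. It ends one year after surgery, about week 7 + 52 = 59. With the pre-surgery scan placed at about week 6, the 6-week schedule gives weeks 0, 6, 14, 20, 26, 32, 38, 44, 50, 56, then every 13 weeks from week 59: 72, 85, 98, 111. That is 14 samples, of which 10 fall by the end of adjuvant treatment.

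**Assumptions.** PFS is exponential with median 12 to 53 months. The documents state no PFS; 53 months is the median overall survival in Section 3.2.1, used as an upper bound. Scheduled sampling ends at progression, every patient reaches surgery, and the baseline sample is always present. Other samples are missed independently at 0% or 5%. Progression samples are not counted.

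**Formulas.** With rate λ = ln 2 / median, k samples, last sample at week T, and miss rate m:

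- complete patients = 37 × exp(−λT) × (1 − m)^(k−1)
- samples used = k × complete patients
- samples collected = 37 × [1 + (1 − m) × Σ exp(−λt)], summed over the visits after baseline
- share discarded = 1 − used / collected

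**Worked case: full schedule, median 12 months (52.18 weeks), none missed.** λ = 0.6931/52.18 = 0.01328 per week. exp(−0.01328 × 111) = 0.229. Complete = 37 × 0.229 = 8.5. Used = 14 × 8.47 = 119. Collected = 305. Discarded = 1 − 119/305 = 61%.

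**The same case with 5% missed.** 0.95^13 = 0.513. Complete = 8.47 × 0.513 = 4.3. Used = 61. Collected = 292. Discarded = 79%.

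| Visits in the model | Missed | Complete of 37 (median PFS 12 → 53 months) | Collected samples discarded |
|---|---|---|---|
| Full schedule, 6-week scans (14 samples, week 111) | 0% | 8.5 → 26.5 | 61% → 18% |
| Same | 5% | 4.3 → 13.6 | 79% → 56% |
| Full schedule, 12-week scans (10 samples, week 111) | 0% | 8.5 → 26.5 | 60% → 17% |
| Same | 5% | 5.3 → 16.7 | 74% → 45% |
| Through end of adjuvant, 6-week scans (10 samples, week 56) | 0% | 17.6 → 31.3 | 32% → 8% |
| Same | 5% | 11.1 → 19.7 | 56% → 39% |
| First three samples (week 14) | 0% | 30.7 → 35.5 | 10% → 2% |

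On the full 6-week schedule with nothing missed, intermediate medians of 18, 24 and 36 months give losses of 46%, 36% and 26%. The loss therefore passes one half somewhere between 12 and 18 months.

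These figures measure lost data. The bias in the marker trend cannot be sized, because the documents give no marker levels, no variances and no relation between marker and progression.

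**The case against.** The strongest objection is that the plan does not say what it is being charged with. Section 8.3 does not state a classical or complete-case analysis, and its wording could be carried out as a mixed model. Nor does it say that every scheduled visit enters. Section 2.3 (objective 2) concerns blood-based changes with treatment, and Section 8.3 plans no analysis of the markers as predictors of progression. An analysis limited to the first three samples would meet much of that objective and lose little.

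This stands, and it limits the point. A reader might infer that the plan keeps only patients with every visit, that most of the data are dropped, and that the trend is estimated in long-term progression-free patients. The documents support none of these as fact. The first is the default of the classical method, not a stated rule. The second needs the full schedule together with either a short PFS or sporadic missed samples, or else a shorter window with both; the documents give neither rate. The third needs all visits to be in the model.

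The objection does not remove the point. The method named, in its usual form, is the complete-case one. The visits are left open, the schedule is unbalanced by design, and the missing-data guidelines that Section 4.7 relies on are not in Section 8.

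A mixed model is also no full cure. It assumes that samples are missing at random given the marker values already observed, and progression is judged on imaging, so that may fail. It can also have trouble converging with 37 patients.

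**Conclusion.** The concern holds in conditional form. As written, the sentence leaves the analysis open. Carried out as classical ANOVA over all scheduled visits, it would be a complete-case analysis selected on outcome, with no place for the progression sample. Under the assumptions above (exponential PFS, median 12 to 53 months, all patients operated), about 8 to 26 of 37 patients would be complete and 61% to 18% of collected samples discarded, rising to 79% to 56% if 5% of samples are missed. Over the first three samples, with none missed, the loss is only 10% to 2%. The range is wide because the window, PFS and missed-sample rate are all unknown.

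The endpoint is exploratory. The MPR test and its power are untouched and no trial decision depends on it. This is a cheap improvement to the plan, not a serious fault.

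**What to change.** Replace the sentence in Section 8.3 with a linear mixed model fitted by REML, using all available scheduled samples from all patients, and state:

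- **Visits.** Name those that enter, as fixed effects. Give windows, or use actual sampling time, for patients who move to 3-monthly imaging.
- **Covariance.** Use a patient random effect or a structured within-patient covariance. An unstructured matrix over 14 visits has 14 × 15 / 2 = 105 parameters, too many for 37 patients. Name a simpler fallback in case of non-convergence.
- **Scale.** Use log values if the distribution is skewed.
- **Missing data.** State that the model assumes missing at random. Add one sensitivity analysis, for example restriction to the neoadjuvant window or a joint model with progression.
- **Progression samples.** Include them by actual sampling time, or summarise them separately. They should not be forced into a scheduled visit.

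The 6-week and 12-week imaging intervals in Table 3 must be reconciled with each other and with Sections 1.1, 5.4 and 7.11, because they fix the number of repeated measures.

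The cost is a short paragraph of text, slightly more analysis work and possible convergence problems. No new data or samples are needed.

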9.0 LABELING, PACKAGING, STORAGE AND RETURN OF CLINICAL SUPPLIES

9.1 Investigational Product

The investigator shall take responsibility for and shall take all steps to maintain appropriate records and ensure appropriate supply, storage, handling, distribution and usage of investigational product in accordance with the protocol and any applicable laws and regulations.

9.2 Packaging and Labeling Information

Clinical supplies will be affixed with a clinical label in accordance with regulatory requirements.

9.3 Clinical Supplies Disclosure

This trial is open-label. Drug identity (name, strength) is included in the label text.

9.4 Storage and Handling Requirements

Clinical supplies must be stored in a secure, limited-access location under the storage conditions specified on the label.

Receipt and dispensing of trial medication must be recorded by an authorized person at the trial site.

Clinical supplies may not be used for any purpose other than that stated in the protocol.

10.0 ADMINISTRATIVE AND REGULATORY DETAILS

10.1 Confidentiality

Individual patient medical information obtained as a result of this study is considered confidential and disclosure to third parties is prohibited with the exceptions noted below. Patient confidentiality will be ensured by using patient identification code numbers. Treatment data may be given to the patient's personal physician or to other appropriate medical personnel responsible for the patient's welfare. Data generated as a result of the study need to be available for inspection on request by the participating physicians, the Drug Manufacturer's representatives, by the IRB and the regulatory authorities.

10.2 Compliance with Financial Disclosure Requirements

Financial Disclosure requirements are outlined in the US Food and Drug Administration

Regulations, Financial Disclosure by Clinical Investigators (21 CFR Part 54) and will be implemented following institutional standards.

10.3 Compliance with Law, Audit and Debarment

The trial will be conducted in an efficient and diligent manner and in conformance with this protocol; generally accepted standards of Good Clinical Practice (e.g., International Conference on Harmonization of Technical Requirements for Registration of Pharmaceuticals for Human Use Good Clinical Practice: Consolidated Guideline and other generally accepted standards of good clinical practice); and all applicable federal, state and local laws, rules and regulations relating to the conduct of the clinical trial.

10.4 Compliance with Trial Registration and Results Posting Requirements

Under the terms of the Food and Drug Administration Modernization Act (FDAMA) and the Food and Drug Administration Amendments Act (FDAAA), the Sponsor of the trial is solely responsible for determining whether the trial and its results are subject to the requirements for submission to the Clinical Trials Data Bank, <http://www.clinicaltrials.gov>. Information posted will allow subjects to identify potentially appropriate trials for their disease conditions and pursue participation by calling a central contact number for further information on appropriate trial locations and trial site contact information.

10.5 Quality Management System

The Principal Investigator will ensure that trial is conducted and data are generated, documented, and reported in compliance with the protocol, accepted standards of Good Clinical Practice, and all applicable federal, state, and local laws, rules and regulations relating to the conduct of the clinical trial.

A quality assurance audit/inspection of this study may be conducted by regulatory authorities. The quality assurance auditor will have access to all medical records, the investigator's study-related files and correspondence, and the informed consent documentation of this clinical study.

The trial will be monitored in the weekly mesothelioma multidisciplinary conference.

10.6 Data Management

Data management will be provided via the cancer clinical trial infrastructure available at the University of Chicago (eVELOS). It is the responsibility of the investigators to record and verify the accuracy of subject data.

12.0 APPENDIX

12.1 ECOG Performance Status

Grade	Description
0	Normal activity. Fully active, able to carry on all pre-disease performance without restriction.
1	Symptoms, but ambulatory. Restricted in physically strenuous activity, but ambulatory and able to carry out work of a light or sedentary nature (e.g., light housework, office work).
2	In bed <50% of the time. Ambulatory and capable of all self-care, but unable to carry out any work activities. Up and about more than 50% of waking hours.
3	In bed >50% of the time. Capable of only limited self-care, confined to bed or chair more than 50% of waking hours.
4	100% bedridden. Completely disabled. Cannot carry on any self-care. Totally confined to bed or chair.
5	Dead.

* As published in Am. J. Clin. Oncol.: *Oken, M.M., Creech, R.H., Tormey, D.C., Horton, J., Davis, T.E., McFadden, E.T., Carbone, P.P.: Toxicity And Response Criteria Of The Eastern Cooperative Oncology Group. Am J Clin Oncol 5:649-655, 1982.* The Eastern Cooperative Oncology Group, Robert Comis M.D., Group Chair.

12.2 Common Terminology Criteria for Adverse Events V5.0 (CTCAE)

The descriptions and grading scales found in the revised NCI Common Terminology Criteria for Adverse Events (CTCAE) version 5.0 will be utilized for adverse event reporting.

(https://ctep.cancer.gov/protocolDevelopment/electronic_applications/ctc.htm#ctc_60)

12.3 Prescribing Information

12.3.1 Nivolumab

https://www.accessdata.fda.gov/drugsatfda_docs/label/2018/125554s058lbl.pdf

12.3.2 Ipilimumab

https://www.accessdata.fda.gov/drugsatfda_docs/label/2020/125377s110lbl.pdf

12.4 EORTC QOL-C30 Quality of Life Survey

<https://www.eortc.org/app/uploads/sites/2/2018/08/Specimen-QLQ-C30-English.pdf>
